3.8.2.4 PFS in patients where PIK3CA mutation status is measured in ctDNA

An analysis of PFS based on local radiology assessments and using RECIST 1.1 criteria for each of (i) patients with *PIK3CA* mutant status and (ii) patients with *PIK3CA* non-mutant status as measured in ctDNA at baseline will be conducted using the same analytical conventions as the primary analysis.

3.8.2.5 Overall response rate

ORR is defined as the proportion of patients with best overall response of confirmed complete response (CR) or confirmed partial response (PR) according to RECIST 1.1 (see Appendix 3 of the study protocol). ORR will be calculated based on the FAS using investigators' review of tumor assessment data for each cohort. Patients with only non-measurable disease at baseline will be part of the analysis and will be included in the numerator only if a complete response was observed.

ORR will be presented along with the exact binomial two-sided 95% confidence interval (Clopper 1934) by treatment arm for the *PIK3CA* mutant and non-mutant cohorts.

In addition, ORR in the subset of patient with measurable disease at baseline will be presented.

As a supportive analysis, ORR will also be summarized based on the central radiology review of tumor data, if the BICR moves to a 100% audit.

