10.5.2.3 Overall Response Rate (ORR)

ORR is defined as the proportion of patients with best overall response of complete response (CR) or partial response (PR) based on local investigator's assessment according to RECIST 1.1. It will be calculated along with the exact binomial two-sided 95% confidence interval ([Clopper 1934](#)) by treatment arm for the *PIK3CA* mutant and non-mutant cohorts. In addition, ORR analyses based on blinded independent central review will be performed, if relevant.

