10.5.2.6 ECOG Performance Status

ECOG performance status will be used to assess physical health of patients. An analysis of the time to definitive deterioration of the ECOG performance status by one category of the score from baseline will be performed using Kaplan-Meier method. A deterioration is considered definitive if no improvements in the ECOG performance status is observed at a subsequent time of measurement during the treatment period following the time point where the deterioration is observed.

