1.2 Objectives

The study objectives and corresponding endpoints as specified in the protocol are provided in [Table 1-1](#).

Table 1-1 Study objectives

Objective	Endpoint	Analysis
Primary		Refer to Section
To determine whether treatment with alpelisib in combination with fulvestrant prolongs PFS compared to treatment with placebo in combination with fulvestrant for patients with PIK3CA mutant status	PFS based on local radiology assessments and using RECIST 1.1 criteria in the PIK3CA mutant cohort	3.8.1
Key secondary		Refer to Section
To determine whether treatment with alpelisib in combination with fulvestrant	OS in the PIK3CA mutant cohort	3.8.2.1

Objective	Endpoint	Analysis
prolongs overall survival (OS) compared to treatment with placebo in combination with fulvestrant for patients with PIK3CA mutant status		
Other secondary		Refer to Section
To establish proof of concept of treatment benefit with alpelisib in combination with fulvestrant with respect to PFS for patients with PIK3CA non-mutant status	PFS based on local radiology assessments and using RECIST 1.1 criteria in the PIK3CA non-mutant cohort	3.8.2.2
To evaluate the two treatment arms with respect to OS for patients with PIK3CA non-mutant status	OS in the PIK3CA non-mutant cohort	3.8.2.3

• To evaluate the two treatment arms and cohorts of interest with respect to overall response rate (ORR), clinical benefit rate.• To evaluate the two treatment arms and cohorts of interest with respect to time to deterioration of ECOG performance status.• To evaluate the safety and tolerability of alpelisib in combination with fulvestrant	
ORR and CBR in each of the PIK3CA mutant and non-mutant cohorts
 
Time to definitive deterioration of the ECOG performance status of the score from baseline in each of the PIK3CA mutant and non-mutant cohorts
 
- Type, frequency and severity of adverse events per CTCAEv4.03- Type, frequency and severity of laboratory toxicities per CTCAEv4.03	
3.8.2.5
 
3.8.2.6
 
3.8.2.8
 
3.9

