3.8.2.6 Clinical benefit rate

Clinical benefit rate is defined as the proportion of patients with a best overall response of CR or PR or SD or Non-CR/Non-PD lasting 24 weeks or more based on local investigator assessment according to RECIST 1.1 criteria.

A patient will be considered to have SD for 24 weeks or longer if a SD response is recorded at 24-1=23 weeks or later from randomization, allowing for the ± 1 week visit window for tumor assessments. Patients with only non-measurable disease at baseline will be part of the analysis and will be included in the numerator only if they achieve a complete response or have a 'Non-CR/Non-PD' response 23 weeks or more after randomization.

CBR will be presented along with the exact binomial two-sided 95% confidence interval (Clopper 1934) by treatment arm for the *PIK3CA* mutant and non-mutant cohorts.

In addition, CBR in the subset of patient with measurable disease at baseline will be presented.

As a supportive analysis, CBR will also be summarized based on the central radiology review of tumor data, if the BICR moves to a 100% audit.

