Patients receiving any further anti-neoplastic therapy before definitive worsening will be censored at the date of their last assessment before the start date of the therapy. Patients that have not worsened as of the cutoff date will be censored at the date of their last assessment before the cutoff.

Patients without baseline ECOG PS or without any post-baseline ECOG PS will be censored at the date of randomization with censoring reason being ‘No baseline score’ or ‘No post-baseline score’, respectively. However, patients without post-baseline ECOG PS who die within 62 days after date of randomization will be counted as having a definitive deterioration of the ECOG PS at the date of death.

This threshold corresponds to twice the protocol defined ECOG assessment interval plus twice the time window around each assessment: (2 x 28 days)+(2 x 3 days), i.e. 62 days.

Kaplan-Meier estimates will be constructed for each treatment arm in each cohort. The median, 25th and 75th percentiles for time to definitive deterioration for each treatment group will be obtained along with 95% confidence intervals.

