4.4.2 Hypothesis and test statistic

For the primary, key-secondary and secondary efficacy endpoints, the comparison between the two treatment groups will be performed using a stratified log-rank test at levels α described in [Section 3.8](#).

The **stratified log-rank** test (strata information will be based on the data obtained from IRT that was utilized for randomization) will be implemented as follows:

General SAS code for the stratified log-rank test

```
PROC LIFETEST data=dataset METHOD=KM;  
BY stratum;  
TIME survtime*censor(1);  
STRATA trt;  
RUN;  
  
/* stratum represents stratum variable (to be included for stratified analysis only);  
survtime represents variable containing event/censor times;  
censor represents censoring variable (1=censored, 0=event);  
trt represents treatment arm variable; */
```

For each of the K=2 strata, the LIFETEST procedure will be run with the STRATA statement including only the treatment variable. The TIME statement will include the survival time and a (right) censoring variable.

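### The plan gives no between-arm estimate for overall response rate or clinical benefit rate, only a separate exact interval in each arm

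*SAP*

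**What the plan says.** SAP 1.2 (Table 1-1) lists the secondary objective "To evaluate the two treatment arms and cohorts of interest with respect to overall response rate (ORR), clinical benefit rate". Protocol Table 3-1 has the same objective. Four sections define the analysis:

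- SAP 3.8.2.5, ORR: "ORR will be presented along with the exact binomial two-sided 95% confidence interval (Clopper 1934) by treatment arm". It also asks for ORR in patients with measurable disease at baseline, and for a central-review summary if the audit is extended to all patients.
- SAP 3.8.2.6, CBR: "CBR will be presented along with the exact binomial two-sided 95% confidence interval (Clopper 1934) by treatment arm", with the same two additions.
- Protocol 10.5.2.3, ORR: "It will be calculated along with the exact binomial two-sided 95% confidence interval", by arm within each cohort.
- Protocol 10.5.2.4, CBR: the same method.

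None of these sections gives a difference, ratio, odds ratio, stratified analysis or test. SAP 3.8.2.7 carries the same conventions over to the analyses by ctDNA mutation status.

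**The concern.** Patients are randomised 1:1 within each cohort, stratified by lung and/or liver metastases and by previous CDK4/6 inhibitor. Evaluating two randomised arms on a binary endpoint calls for an estimate of the difference between them and its uncertainty. Two one-sample intervals provide neither, and they leave the stratification unused.

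Two things follow. A reader shown two intervals side by side tends to judge by whether they overlap, which is a poor guide to the difference. And if a contrast is wanted later, its scale, stratification and population would have to be chosen after unblinding.

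**Working it through.** **1. Does another section supply the contrast?** SAP 4.4.2 states "For the primary, key-secondary and secondary efficacy endpoints, the comparison between the two treatment groups will be performed using a stratified log-rank test". It sits under 4.4, which covers time-to-event analyses, and a log-rank test cannot be applied to a response proportion. SAP 4.4.4 gives a Cox hazard ratio, also for time-to-event data. SAP 4.3 names one-sided tests for PFS and OS only. No readable general section reaches ORR or CBR.

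**2. How are comparable endpoints handled?** PFS has a stratified Cox hazard ratio in each cohort (SAP 3.8.1.4), and so does OS (3.8.2.1 and 3.8.2.3). Time to 10% deterioration in global health status has a stratified log-rank test and a Cox hazard ratio, and the longitudinal quality-of-life model gives differences in least-squares means with 95% CIs (3.8.2.9). Protocol 10.5.4 rules out formal tests for patient-reported outcomes and still plans a hazard ratio. Standing outside formal testing did not prevent an effect estimate there.

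**3. Is there a stated figure to reproduce?** No. The documents give no power, alpha or effect size for ORR or CBR.

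**4. Illustration.** Arm sizes come from SAP 3.14: 340 patients 1:1 in the mutant cohort (170 per arm) and 220 in the non-mutant cohort (110 per arm). The response rates are assumptions.

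- Per arm: exact Clopper-Pearson 95% interval.
- Contrast: d = p2 - p1, SE = sqrt[p1(1-p1)/n + p2(1-p2)/n], 95% CI = d ± 1.96 SE. This is unstratified and is used only to show the principle.

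For 10% vs 20% at 170 per arm (17 and 34 responders):

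- exact intervals 5.9-15.5% and 14.3-26.8%, which overlap between 14.3% and 15.5%;
- SE = sqrt[(0.09 + 0.16)/170] = 0.0383, half-width 1.96 × 0.0383 = 0.075;
- difference 0.100, 95% CI 0.025 to 0.175, which excludes zero.

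For the same rates at 110 per arm (11 and 22 responders):

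- exact intervals 5.1-17.2% and 13.0-28.7%, which overlap;
- SE = sqrt(0.25/110) = 0.0477, half-width 0.093;
- difference 0.100, 95% CI 0.007 to 0.193, which excludes zero.

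The precision of a 10-point difference across assumed rates:

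| Rates | Half-width, 170 per arm | Half-width, 110 per arm |
|---|---|---|
| 10% vs 20% | 7.5 points | 9.3 points |
| 20% vs 30% | 9.1 points | 11.4 points |
| 40% vs 50% | 10.5 points | 13.1 points |

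These half-widths are the information about the treatment effect that the planned tables would not show.

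**The case against.** **The wording of the objectives supports a descriptive treatment.** Both documents ask whether treatment prolongs PFS and OS in the mutant cohort, and use the weaker verb, evaluate, for ORR, CBR, ECOG status, safety and quality of life. Neither document promises a test of ORR or CBR. This stands: there is no broken commitment and no error-rate problem. It does not remove the gap, because an estimate with an interval is itself descriptive.

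**Any reader can compute the unstratified difference from the per-arm counts.** True, but the stratified estimate cannot be recovered from those counts, and leaving the contrast to readers fixes neither scale nor method in advance.

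**Table layouts are in a separate shells document** (SAP Section 1), which is not available here. The conclusion is therefore confined to the readable plan.

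Three stronger inferences are tempting, and the documents do not support them:

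- *That ECOG deterioration also lacks a contrast.* Its objective has the same form, "To evaluate the two treatment arms and cohorts of interest with respect to time to deterioration of ECOG performance status", and SAP 3.8.2.8 says only "Kaplan-Meier estimates will be constructed for each treatment arm in each cohort", in line with the Kaplan-Meier analysis in Protocol 10.5.2.6. But it is a secondary time-to-event endpoint, so the log-rank comparison in SAP 4.4.2 and the hazard ratio in 4.4.4 reach it.
- *That SAP 4.4.2 is wrong and should be cut back to PFS and OS.* It lies within the time-to-event section and does not purport to cover binary endpoints. Cutting it back would conflict with the log-rank test for quality-of-life deterioration in 3.8.2.9.
- *That the plan loses a calculable amount of power.* Setting the chance of non-overlapping intervals against the power of a test would score a decision rule the plan never adopts. Inputs are also thin: the phase I partial response rates with the combination were 24% in mutant and 0% in non-mutant tumours (Protocol 1.2.3.3), so the mutant figure cannot be carried into the non-mutant cohort.

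**Conclusion.** The point holds for ORR and CBR as a gap in estimation and reporting. Following the readable plan would yield response and benefit rates for each arm, but no treatment effect, no interval for one, and no use of the two stratification factors. At the planned arm sizes the missing 95% interval for a 10-point difference would have a half-width of about 7.5 to 10.5 points in the mutant cohort and 9.3 to 13.1 points in the non-mutant cohort, assuming rates between 10% and 50% and no stratification. The overlap example shows that separate intervals do not stand in for a contrast; it does not predict the trial's result. The alpha-controlled hierarchy, the sample size and the PFS and OS conclusions are unaffected.

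**What to change.** In SAP 3.8.2.5 and 3.8.2.6, and in Protocol 10.5.2.3 and 10.5.2.4, keep the per-arm Clopper-Pearson intervals. Add the between-arm difference in ORR and in CBR with a two-sided 95% CI, stratified by the two randomisation factors as recorded in IRT, using Mantel-Haenszel weights. Do this in each cohort, for the FAS and for the subset with measurable disease at baseline. Label the results descriptive and outside the alpha-controlled hierarchy, with no p-value.

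Leave SAP 4.4.2 unchanged. For ECOG deterioration, at most add a cross-reference in 3.8.2.8 to the Cox hazard ratio in 4.4.4.

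The cost is some wording and a few table rows from data already collected. The small downside is a handful of extra unadjusted estimates, which the labelling addresses.

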3.8.2.6 Clinical benefit rate

Clinical benefit rate is defined as the proportion of patients with a best overall response of CR or PR or SD or Non-CR/Non-PD lasting 24 weeks or more based on local investigator assessment according to RECIST 1.1 criteria.

A patient will be considered to have SD for 24 weeks or longer if a SD response is recorded at 24-1=23 weeks or later from randomization, allowing for the ± 1 week visit window for tumor assessments. Patients with only non-measurable disease at baseline will be part of the analysis and will be included in the numerator only if they achieve a complete response or have a 'Non-CR/Non-PD' response 23 weeks or more after randomization.

CBR will be presented along with the exact binomial two-sided 95% confidence interval (Clopper 1934) by treatment arm for the *PIK3CA* mutant and non-mutant cohorts.

In addition, CBR in the subset of patient with measurable disease at baseline will be presented.

As a supportive analysis, CBR will also be summarized based on the central radiology review of tumor data, if the BICR moves to a 100% audit.

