10.5.2.4 Clinical benefit rate

Clinical benefit rate is defined as the proportion of patients with a best overall response of CR or PR or SD or Non-CR/Non-PD lasting more than 24 weeks based on local investigator assessment. It will be calculated along with the exact binomial two-sided 95% confidence interval ([Clopper 1934](#)) by treatment arm for the *PIK3CA* mutant and non-mutant cohorts. In addition, clinical benefit rate analyses based on blinded independent central review will be performed, if relevant.

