Example: In a case where confirmation of response is required the sum of lesion diameters is 200 mm at baseline and then 140 mm - 150 mm - 140 mm - 160 mm - 160 mm at the subsequent visits. Assuming that non-target lesions did not progress, the overall lesion response would be PR - SD - PR - PR - PR. The second assessment with 140 mm confirms the PR for this patient. All subsequent assessments are considered PR even if tumor measurements decrease only by 20% compared to baseline (200 mm to 160 mm) at the following assessments.

If the patient progressed but continues study treatment, further assessments are not considered for the determination of best overall response.

Note: these cases may be described as a separate finding in the CSR but not included in the overall response or disease control rates.

The best overall response for a patient is always calculated, based on the sequence of overall lesion responses. However, the overall lesion response at a given assessment may be provided from different sources:

- Investigator overall lesion response
- Central Blinded Review overall lesion response
- Novartis calculated overall lesion response (based on measurements from either Investigator or Central Review)

The primary analysis of the best overall response will be based on the sequence of investigator/central blinded review/calculated (investigator)/calculated (central) overall lesion responses.

Based on the patients' best overall response during the study, the following rates are then calculated:

Overall response rate (ORR) is the proportion of patients with a best overall response of CR or PR. This is also referred to as 'Objective response rate' in some protocols or publications.

Disease control rate (DCR) is the proportion of patients with a best overall response of CR or PR or SD. The objective of this endpoint is to summarize patients with signs of "activity" defined as either shrinkage of tumor (regardless of duration) or slowing down of tumor growth.

Clinical benefit rate (CBR) is the proportion of patients with a best overall response of CR or PR, or an overall lesion response of SD or Non-CR/Non-PD which lasts for a minimum time duration (with a default of at least 24 weeks in breast cancer studies). This endpoint measures signs of activity taking into account duration of disease stabilization.

Another approach is to summarize the progression rate at a certain time point after baseline. In this case, the following definition is used:

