2.4.3 Best overall response (BOR)

The evaluation of BOR will be assessed using RECIST 1.1. The definitions and the details on the derivation of BOR are given in Appendix 3 of the study protocol.

The best overall response will usually be determined from response assessments undertaken while on treatment. In addition, only tumor assessments performed before the start of any further anti-neoplastic therapies (i.e. any additional secondary anti-neoplastic therapy with the exception of palliative radiotherapy) will be considered in the assessment of BOR.

Further anti-neoplastic therapies will be identified from the data collected on ‘Antineoplastic therapy since discontinuation of study treatment- Medication’ eCRF and “Antineoplastic Therapy - Radiotherapy” eCRF.

Palliative radiotherapy is the only setting of radiotherapy allowed during a study. It will not be considered as an antineoplastic therapy for the assessment of BOR.

Continuation of fulvestrant monotherapy as 1st new anti-neoplastic therapy after end of treatment without prior PD and collected in the ‘antineoplastic therapy since discontinuation of study treatment- Medication’ eCRF, will not be considered as an anti-neoplastic therapy for the assessment of BOR.

Since the tumor assessments are performed every 8 weeks (+/- 7 days) after randomization during the first 18 months and every 12 weeks (+/- 7 days) thereafter, the standard definition of a best overall response evaluation of “stable disease”, “progressive disease” or “unknown” given in the Appendix 3 of the study protocol requires an adjustment. Best overall response for each patient is determined from the sequence of overall (lesion) responses according to the following rules:

- CR = at least two determinations of CR at least 4 weeks apart before progression
- PR = at least two determinations of PR or better at least 4 weeks apart before progression (and not qualifying for a CR)
- SD = at least one SD assessment (or better) > 7 weeks after randomization date (and not qualifying for CR or PR).
- Non-CR/non-PD = at least one non-CR/non-PD assessment (or better) > 7 weeks after randomization date (and not qualifying for CR or PR). This applies only for patients with non-measurable disease alone at Baseline.
- PD = progression ≤ 17 weeks after randomization date (and not qualifying for CR, PR, SD or non-CR/non-PD).

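### The SAP's 24-week rule for stable disease omits 'or better', so a patient with best response SD whose only evaluable scan from week 23 on is an unconfirmed PR or CR can be scored as no clinical benefit

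*SAP*

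**What the plan says.** **Definition.** In SAP 3.8.2.6 a patient contributes to CBR when the best response falls in this list: "CR or PR or SD or Non-CR/Non-PD lasting 24 weeks or more based on local investigator assessment".

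**Operational rule for SD.** The same section then says: "A patient will be considered to have SD for 24 weeks or longer if a SD response is recorded at 24-1=23 weeks or later", counted from randomization. The one-week allowance is explained by the scan window.

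**Operational rule for non-measurable disease only.** These patients enter the numerator only if they reach a complete response or "have a 'Non-CR/Non-PD' response 23 weeks or more after randomization".

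**Best overall response.** SAP 2.4.3 requires confirmation of a response: "PR = at least two determinations of PR or better at least 4 weeks apart before progression (and not qualifying for a CR"), with the parallel requirement for CR. For stable disease it says: "SD = at least one SD assessment (or better) > 7 weeks after randomization date (and not qualifying for CR or PR"). Non-CR/Non-PD is defined the same way, also with the words *or better*.

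**Threshold wording elsewhere.** Protocol 10.5.2.4 has "CR or PR or SD or Non-CR/Non-PD lasting more than 24 weeks based on local investigator assessment". Protocol Appendix 3 (14.3.17) describes a minimum duration "with a default of at least 24 weeks in breast cancer studies".

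**The concern.** An unconfirmed PR or CR falls back to a best response of SD, because SAP 2.4.3 accepts an SD assessment or better. To count towards CBR, that SD must then last 24 weeks. The rule that decides this looks for an SD record and does not say what to do with a PR or CR record at the same time point.

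Read literally, a better scan can give a worse classification: SD at week 24 counts, and a first, unconfirmed PR at week 24 may not. A benefit measure should not be able to run backwards in that way.

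What is at stake is the reproducibility of a listed secondary endpoint in both cohorts. Two programmers could derive different values from the same data. The rule also carries over to the measurable-disease subset, to the analysis by ctDNA mutation status (SAP 3.8.2.7) and to any central-review CBR.

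**Working it through.** **Inputs**

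- Scan schedule (SAP 2.4.3): "tumor assessments are performed every 8 weeks (+/- 7 days) after randomization during the first 18 months". Scans therefore fall at weeks 8, 16, 24, 32 and 40.
- CR or PR needs two determinations at least 4 weeks apart (SAP 2.4.3).
- SD counts as lasting if an SD is recorded at week 23 or later (SAP 3.8.2.6).
- Planned cohort sizes are 340 (mutant) and 220 (non-mutant), randomized 1:1 (Protocol 4.1).

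**Step 1. The plan's own cut-off.** The week-24 scan less the 1-week window is 24 − 1 = 23 weeks. This reproduces.

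**Step 2. Trace four patients with measurable disease.**

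| Wk 8 | Wk 16 | Wk 24 | Wk 32 | Best response | SD record at ≥ 23 wk? | Literal CBR | CBR with *or better* |
|---|---|---|---|---|---|---|---|
| SD | SD | SD | PD | SD | yes | yes | yes |
| SD | SD | PR | PD | SD (PR unconfirmed) | no | **no** | yes |
| SD | SD | PR | SD | SD (PR unconfirmed) | yes, wk 32 | yes | yes |
| SD | SD | PR | PR | PR (confirmed) | not needed | yes | yes |

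Rows 1 and 2 differ only at week 24, and the patient with the better scan scores worse. Row 3 is realistic: Protocol 14.3.17 says that a single PR which is lost without progression is followed by a status of SD.

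**Step 3. How narrow is the gap?** Fix PR at week 24 and let every other scan be SD, PR, unknown (UNK) or terminal PD. Any second PR would fall at least 8 weeks away and confirm the response, so keep only sequences with no other PR.

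- Weeks 8 and 16: each SD or UNK, giving 2 × 2 = 4 patterns.
- Weeks 32 and 40: SD–SD, SD–PD, SD–UNK, UNK–SD, PD, UNK–PD and UNK–UNK, giving 7 patterns.
- Total: 4 × 7 = 28 sequences with best response SD and an unconfirmed PR at week 24.
- The first four late patterns contain an SD after week 23: 4 × 4 = 16 count under the literal rule.
- The last three do not: 4 × 3 = 12 fail under the literal rule.
- With *or better*, all 28 count.

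These are counts of possible sequences, not proportions of patients. Follow-up that ends early behaves like the UNK–UNK pattern. That can arise because assessments after new anti-neoplastic therapy are left out of best response (SAP 2.4.3) and data after the cut-off are not used (SAP 2.2).

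**Step 4. Non-measurable disease only.** An unconfirmed CR at week 24 followed by PD gives a best response of Non-CR/Non-PD under SAP 2.4.3. Whether it counts depends on whether achieving a complete response in 3.8.2.6 includes an unconfirmed one, which that section does not say.

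**Step 5. Size per patient.**

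- Mutant cohort: 340/2 = 170 per arm, and 1/170 = 0.59 percentage points.
- Non-mutant cohort: 220/2 = 110 per arm, and 1/110 = 0.91 percentage points.
- With the 341 and 231 patients actually randomized (Protocol, Amendment 5), the figures are about 1/170.5 = 0.59 and 1/115.5 = 0.87.

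**Step 6. Threshold wording.** The week-24 window runs from 23 × 7 = day 161 to 25 × 7 = day 175, which is 15 days, and week 24 itself is day 168. *If* duration is measured to the day of that scan, the SAP rule accepts all 15 days, Appendix 3 taken without a window accepts 8, and Protocol 10.5.2.4 accepts 7. None of the three texts says that duration ends at the scan.

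**The case against.** The strongest answer is that the SAP sentence says *if*, not *only if*. The governing definition is a best response of SD that lasts 24 weeks or more, and best response of SD already includes *or better*. On that view the text allows the patient in row 2 to be counted. This stands as far as it goes, and it is why the finding is that such a patient *can* be scored as no benefit. It does not dispose of the point, because this sentence is the only operational rule for the duration of SD and a program written from it would look for an SD record.

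Four stronger readings are tempting, and the documents do not support them.

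- *That CBR counts only recorded SD.* Confirmed CR and PR count whatever their duration, and Non-CR/Non-PD has its own rule.
- *That every unconfirmed PR at week 24 is lost.* A later SD record rescues the patient and a later PR confirms the response. Of the 28 sequences above, 16 already count.
- *That the 24-week wordings give CBR two materially different values.* The SAP definition agrees with Appendix 3; only Protocol 10.5.2.4 is worded differently. If SD lasts until documented progression, a patient with SD at week 24 and PD at week 32 satisfies all three. Any size put on the difference would need an assumed duration rule and an assumed spread of scan days.
- *That the comparison between arms is biased.* This would need the frequency of late unconfirmed responses in each arm, which the documents do not give.

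**Conclusion.** The gap is real and narrow. On the literal wording of SAP 3.8.2.6, a patient is dropped from CBR when three things hold together: best response is SD, the only evaluable non-progression record from week 23 on is an unconfirmed PR or CR, and that record is followed by PD or by no further evaluable SD or confirming scan. The same patient with SD at that scan would count.

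The size is about 0.6 points per affected patient in a mutant-cohort arm and 0.9 points in a non-mutant-cohort arm, at the planned arm sizes. The number affected cannot be derived from the documents, and no direction of effect between arms is claimed. The conclusion assumes that the derivation follows the sentence as written.

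CBR is reported by arm with exact confidence intervals, is not formally tested and spends no alpha, so the primary and key secondary conclusions are untouched. The point is still worth fixing, because a stated rule should not score a better scan worse. The difference in threshold wording is a note for tidying, not a second finding.

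**What to change.** 1. In SAP 3.8.2.6, reword the SD rule so that SD lasts 24 weeks or longer when *SD (or better) is recorded at 23 weeks or later from randomization and before progression*. For patients with non-measurable disease only, use *Non-CR/Non-PD (or better)* in the same way.
2. Apply this in the CBR derivation. If the program already treats PR or CR at or after week 23 as sufficient, record that and align the text with it.
3. Add one sentence to the SAP stating that the 24-weeks-or-more definition with the 1-week scan window governs.

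The cost is two or three sentences in the SAP and a check of one derivation, with no new data. A protocol change is not needed for this. It would require a written amendment and the approvals described in Protocol 12.1, so the wording of Protocol 10.5.2.4 can wait for any amendment made for other reasons.
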